Objectives	Primary objective Assess the rates of BSI from the use of 3CBs (e.g., SmofKabiven [®] , Kabiven [®] , others) compared to hospital compounded bags (HCBs) in patients requiring PN in Spanish hospitals
	 Secondary objectives Determine the extent of treatment requirement in patients receiving 3CBs compared to hospital compounded bags Assess mortality rate in patients receiving 3CB compared to patients receiving HCBs Evaluate the influence of additions made to the PN bags on BSI rates Assess the effect of manual versus automated compounding on BSI rates Evaluate the rate of PN-associated adverse events in patients receiving 3CBs compared to HCBs, including sepsis, organ failure, metabolic impairment, hepatic dysfunction and electrolyte imbalance Assess the achievement of the nutritional target in patients receiving 3CBs compared to HCBs
Investigational sites	Approximately 10 sites using 3CBs and/or HCBs
Study design	Retrospective observational data retrieval in a two-step design: In step 1, data from 30% of the target patient number will be obtained from the investigational sites to evaluate study feasibility and perform an interim analysis assessing statistical power.In step 2, the study will be continued by documenting further 70% of patients if the statistical power is > 60%.
Observational drug	Any PN administered in 3CBs, containing all three major macronutrients (glucose, amino acids, lipids)
Comparator	Hospital compounded PN bags containing all three major macronutrients
Patients	Adult hospitalized patients receiving PN in Spain, treated on any ward and by any medical discipline within the hospital (intensive care unit, normal ward; surgery, non-surgery)

Outcome parameters Primary outcome parameter

 BSI only with concomitant antimicrobial treatment (bacteria and/or candida), thereby excluding patients with contaminations

Secondary outcome parameters

- Rate of peripheral line associated BSI
- Rate of central line associated BSI
- Single organ failure, multiple organ failure
- Mortality
- PN-related adverse events of special interest: metabolic impairment (hyperglycemia, hypertriglyceridemia), hepatic dysfunction (cholestasis: transaminases, gamma-glutamyl transferase, alkaline phosphatase, bilirubin), electrolyte imbalance (sodium, potassium, chloride, calcium, phosphate, bicarbonate)
- Changes in prealbumin, C-reactive protein
- Achievement of caloric target (hypo-, hyperalimentation)
- Extent of treatment requirement: Hospital length of stay, ICU length of stay, antibiotics, antimycotics, vasopressors and mechanical ventilation

These parameters will be documented for the multivariate analysis - if available - and the discussion. These are not outcome parameters:

- Demographic data: gender, age, weight (BMI)
- Admission type: elective, emergency, transferral
- Reason for hospital admission: leading diagnosis
- Reason for ICU admission: surgical, medical, trauma
- Primary disease
- Duration of hospitalization before venous catheter (VC) placement and PN
- Type of venous access: central, peripheral
- VC insertion and maintenance according to "Bacteremia Zero" protocol
- Type of hospital compounding: automated, manual
- VC related influence: number of VC; number of lumen of VC; site of VC placement (jugular, subclavian, femoral); insertion of VC in ER, OR, ICU; clinical experience of staff placing and handling VC and PN; duration of VC; duration of PN and duration between VC placement and PN; SOP for hygiene in place (cap, mask, sterile gloves sterile full body drape)
- Indication for PN
- Percentage of PN (supplemental PN, total PN)
- Omega-3 fatty acids and glutamine as active ingredients

- Additions of vitamins, trace elements and/or electrolytes to PN bag
- Addition to PN bag made under sterile conditions in the pharmacy, or on the ward
- Co-morbidities: cancer, malabsorption, pancreatitis, liver failure, renal failure, diabetes, malnutrition (SGA), gastrointestinal disorder
- Enteral, oral nutrition, oral nutritional supplements
- Antibiotic and antimycotic treatment (number, duration, antibiotic free days)
- Availability of a Nutrition Support Team at the center
- Hospital characteristics: region, teaching status, urban/ rural, number of beds
- APR-DRG severity of illness
- APACHE II score or SAPS II score

Inclusion criteria

General:

- Adult patients \geq 18 years
- Hospitalized between 1. January 2014 and 31. December 2015

Study-specific:

- PN for at least three consecutive days
- PN as 3CBs or hospital compounded, containing all three major macronutrients
- complete medical record regarding treatment information, PN administration details and, if applicable, adverse events

Exclusion criteria

General

Prior participation in this study

Study specific

- BSI at admission to the participating hospital (not hospitalacquired), i.e., prior to the 3rd calendar day of admission
 - where day of admission is calendar day 1
- Immunosuppression due to concomitanttherapy (e.g. immunosuppressive therapy due to transplantation, use of glucocorticoids)or disease (e.g. HIV, leukemia)
- persisting vascular access (port, shunts for dialysis) used during PN episode
- femoral venous placement of central venous line
- burns (irrespective of severity), extensive skin injuries (e.g., Lyell's disease)
- chemo-/ radiotherapy during hospital admission period or up to 3 months before hospital admission
- change of PN delivery method during study period, e.g., from compounding to 3CBs (change of dosing and/or frequency during the observational period is allowed)

Sample size	The sample size must allow the comparison of BSI rates associated with three chamber bags with those associated with hospital compounded bags. Due to the high variability among studies reported in the literature, a mean scenario is considered based on the incidence of BSI infections reported in Spain [Bonet 2005; Aguilella 2012], i.e., an overall incidence of BSI of 12.3% with a difference between the groups of 3% (± 1.5%). Samples size are estimated assuming incidence rates of BSI in MCB of 10.8% and 13.8% in hospital compounded PN, respectively. A sample of 1891 patients per PN type (3782 patients in total) is required taking into account a significance level of 0.05, the influence of the interim analysis on statistical power, and a statistical power of 0.80.
Statistical analysis	Interim analysis: The study is run in a 2 stage group sequential design with an interim analysis (IA) after acquiring 30% of the total sample size. This allows a premature discontinuation if BSI rates and their difference, i.e., the actual power of the study, are substantially lower than planned. The study will be terminated after the IA if the conditional power based on the IA results will be smaller than 60%.
	Final analysis: Baseline demographics, co-morbidities and hospitalization characteristics will be reported descriptively by means of standard deviations and medians with ranges for continuous variables and by counts and percentages for categorical variables. Incidence rates for BSI will be reported by treatment group. Multivariate logistic regression will be used to create a model to estimate the risk of BSI. The model will be adjusted for covariables as risk factors, potential confounders, baseline differences, etc. As variable-selection method correlations will be calculated for the rough selection and then backward elimination selection will be applied in the logistic regression model with a significance level of 10%. The risk of BSI will be reported as adjusted odds ratios with 95% confidence limits. For secondary/ further variables multivariate regression models will be used.
Observation period	Length of stay at the participating hospital
Planned start and end	Data retrieval for step 1: September 2016 – January 2017 Data retrieval for step 2: March – June 2017
Principal investigator	[name] PhD Madrid, Spain

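### The manual-versus-automated compounding objective is planned as a patient-level analysis over at most about 10 hospitals; if method is largely fixed by hospital, its 95% limits are too narrow and the contrast is confounded with hospital

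*Combined protocol and SAP*

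**What the plan says.** The Objectives row of the combined protocol and SAP lists "Assess the effect of manual versus automated compounding on BSI rates" as a secondary objective. Under Investigational sites the study has "Approximately 10 sites using 3CBs and/or HCBs". The hospitals that can inform this objective are therefore at most about 10, and fewer if some use only 3CBs.

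The list of parameters documented for the multivariate analysis includes "Type of hospital compounding: automated, manual". It does not say whether this is recorded per patient, per hospital or per period. A separate entry reads "Hospital characteristics: region, teaching status, urban/ rural, number of beds", and the presence of a nutrition support team at the centre is also listed.

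Under Statistical analysis, final analysis, the risk of BSI is modelled by multivariate logistic regression with backward elimination at the 10% level and reported as adjusted odds ratios with 95% confidence limits. The row closes with "For secondary/ further variables multivariate regression models will be used". No hospital term, random effect, generalised estimating equation or robust variance appears anywhere. No sample size, power or number of hospitals per method is given for this objective.

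**The concern.** A logistic regression that ignores hospital treats every HCB patient as an independent piece of information about compounding method. If a pharmacy compounds mostly one way, patients of the same hospital share the same value of the method variable, and there is little or no comparison within hospitals. The coefficient is then a difference between two small sets of hospitals. Its precision depends on how many hospitals there are and how much they differ in BSI, not on the number of patients.

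Two things follow. The 95% limits are too narrow whenever hospitals differ in BSI for reasons the model does not capture. The estimate also cannot be told apart from other features that differ between the two sets of hospitals: with one method per hospital, fixed hospital effects would be fully collinear with method.

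At stake is an odds ratio reported as an effect of compounding method when it may only reflect which hospitals took part. The Study rationale already presents automated compounding as better than manual, so a chance result in that direction would easily be read as confirmation.

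**Working it through.** **Inputs from the documents.** The Sample size row gives the rates: "Samples size are estimated assuming incidence rates of BSI in MCB of 10.8% and 13.8% in hospital compounded PN, respectively". The same row sets two equal groups of 1891 (3782 overall), alpha 0.05 and power 0.80. About 10 sites in total.

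**The plan's own figure.** For 13.8% versus 10.8%, two-sided 5%, 80% power and pooled variance, the usual two-proportion formula gives 1881 per group against the stated 1891, so that figure reproduces. It applies to 3CB versus HCB only. It also fixes the number available here: about 1891 HCB patients.

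**Assumptions, not in the documents.** One method per hospital; 10 or 6 HCB hospitals of equal size, half on each method; intra-hospital correlation (ICC) from 0.001 to 0.02; no true difference between methods.

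**Error rate of the patient-level test.** With m = 1891 / (number of hospitals), the variance is inflated by DE = 1 + (m − 1) × ICC. A nominal 5% test then has true error 2 × [1 − Φ(1.96 / √DE)]. For 10 hospitals m = 189.1; for 6, m = 315.2. Example with 10 hospitals and ICC 0.01: DE = 1 + 188.1 × 0.01 = 2.88; 1.96 / √2.88 = 1.155; error = 25%. The between-hospital SD is √(ICC × 0.138 × 0.862).

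| ICC | Between-hospital SD (points) | 10 hospitals: DE, error | 6 hospitals: DE, error |
|---|---|---|---|
| 0.001 | 1.1 | 1.19, 7% | 1.31, 9% |
| 0.005 | 2.4 | 1.94, 16% | 2.57, 22% |
| 0.01 | 3.4 | 2.88, 25% | 4.14, 34% |
| 0.02 | 4.9 | 4.76, 37% | 7.28, 47% |

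Beta-binomial simulation (20,000 runs per setting, pooled two-proportion test) agrees within about 1 point. A t test on hospital rates stays at 4.6-5.3% wherever each method has at least two hospitals. In most settings, unequal hospital sizes raise the patient-level error by up to about 4 points.

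**If some sites use both methods.** Take 10 hospitals and ICC 0.01.
- Four sites split equally and six single-method: only 0.6 of the between-hospital variance enters the contrast. The inflation is 0.99 + 0.01 × 0.6 × 189.1 = 2.12, and the error falls from 25% to about 18%.
- Every site mixed, half at 70/30 and half at 30/70: the share is (0.7 − 0.3)² = 0.16. The inflation is 0.99 + 0.01 × 0.16 × 189.1 = 1.29, and the error is about 8%.

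**What a hospital-level analysis can detect.** With 5 versus 5 hospitals, SE = √(2/5 × 0.138 × 0.862 × DE / 189.1). At ICC 0.01 this is 0.0269. With 8 degrees of freedom, 80% power needs about 3.20 SE, or 8.6 points. At ICC 0.005 and 0.02 the figures are 7.1 and 11.1 points. Power for a 3-point difference is 22%, 16% and 12% at ICC 0.005, 0.01 and 0.02. With 3 versus 3 hospitals the detectable difference is 9.6 to 16.1 points over the same range.

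**The case against.** The strongest reply is that the size of the problem rests on inputs the plan does not contain.

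- **One method per hospital.** A reader might infer that compounding method is a property of the pharmacy, so that separating it from hospital is impossible. The documents do not say this. Compounding type is listed apart from the hospital characteristics, and nothing rules out a site that used both methods or changed during 2014-2015. The mixed-site figures show that this matters. It makes the point conditional.
- **The ICC.** A reader might also infer that a false effect will often be declared. At an ICC of 0.001 the error is only 7-9%, so how often depends on an unknown.
- **Unadjusted simulation.** The planned model may include severity scores, venous access, adherence to the catheter protocol, hygiene procedures and where additions are made. So far as these explain differences between hospitals, the residual correlation falls by an unknown amount. The figures are therefore illustrations, not predictions for the adjusted model.
- **Elimination.** It is tempting to say that the hospital-level covariates would use up the few between-hospital degrees of freedom and leave the coefficient to the elimination procedure. No calculation here included those covariates or the elimination step, so that is not claimed.
- **The analysis is inferred.** No test or success rule is set for this objective, and the sentence on secondary variables may mean outcomes other than BSI. That leaves the main logistic model for BSI as the natural reading. Either way it is a patient-level regression that reports limits without hospital.

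None of this supplies the missing allowance for hospital. Any residual between-hospital variation makes the limits too narrow if method follows hospital, and the plan has no step to find out whether it does.

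**Conclusion.** The point holds in conditional form. Followed as written, the plan gives an interval for manual versus automated compounding that ignores hospital. If method is mostly constant within hospitals, that interval is too narrow and the estimate is a confounded comparison of at most about 10 hospitals. The unadjusted error of a nominal 5% test runs from 7-9% (ICC 0.001) to 37-47% (ICC 0.02) for 10 to 6 hospitals. Both the ICC and the one-method premise are assumptions, and adjustment or mixed sites would reduce these figures.

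A reader might extend this to the main 3CB versus HCB result or to the stated sample size. Nothing here supports that: the calculation concerns only the contrast within HCB patients, and the sample size reproduces for its own comparison. For an unpowered secondary objective, the change should be made but does not threaten the study.

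**What to change.** 1. Restrict this objective to HCB patients, since method has no value for 3CB patients.
2. Record compounding method for each hospital and period, and report the number of hospitals and the BSI rate by hospital for each method.
3. Base the interval on hospitals. Either compare hospital rates, standardised for patient-level covariates, by a t test on (HCB hospitals − 2) degrees of freedom, or fit a random-hospital model with a small-sample correction. Where a site used both methods, use its within-hospital contrast.
4. If one method is represented by a single hospital, between-hospital variation within that method cannot be estimated. Report the rates descriptively without a test.
5. Label the result an exploratory comparison of hospitals, not an effect of method. This step is needed because the hospital-level analysis repairs the error rate but not the confounding with other hospital features.

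The cost is wording, one recorded item, and a much wider interval: with 5 versus 5 hospitals only differences of about 7 to 11 points would be detectable with 80% power at ICC 0.005 to 0.02. No extra patients are needed. The plan should state this low power openly.

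### Neither the sample size nor the primary logistic model allows for dependence within about 10 hospitals, so the 95% limits may be too narrow and power below 80%

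*Combined protocol and SAP*

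**What the plan says.** The Investigational sites row gives "Approximately 10 sites using 3CBs and/or HCBs" and does not say how many sites fall into each category. An exclusion criterion removes patients with a "change of PN delivery method during study period, e.g., from compounding to 3CBs". This suggests that some hospitals have both types available, but it does not rule out single-type hospitals.

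The Sample size row states: "A sample of 1891 patients per PN type (3782 patients in total) is required". The only ingredients it lists are the assumed rates (10.8% and 13.8%), the 0.05 level, the interim analysis and 80% power.

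Under Statistical analysis, "Multivariate logistic regression will be used to create a model to estimate the risk of BSI". Results are adjusted odds ratios with 95% limits, and the variance estimator is not specified. Covariates are screened by correlation, and then "backward elimination selection will be applied in the logistic regression model with a significance level of 10" per cent.

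Hospital-level items are among the candidates, for example "Hospital characteristics: region, teaching status, urban/ rural, number of beds", along with hygiene procedures, the catheter-care protocol and a nutrition support team. Of the whole list the plan says: "These parameters will be documented for the multivariate analysis - if available - and the discussion".

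For the interim: "The study will be terminated after the IA if the conditional power based on the IA results will be smaller than 60" per cent.

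Nowhere does the plan mention a site effect, stratification by site, a clustered variance, an ICC or a design effect.

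**The concern.** Patients in one hospital share catheter practice, hygiene rules, staff and compounding method. The plan itself treats these as influences on bloodstream infection (BSI). If hospitals also differ in which PN type they use, part of the comparison between bags is a comparison between a handful of hospitals. A model that counts each patient as independent then overstates the information, and its limits are too narrow.

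A difference between hospitals could be reported as an effect of the bag. According to the Study rationale, the result is meant to feed a pharmaco-economic model, so the error would carry forward. The 60% conditional-power rule depends on the same unstated variance.

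**Working it through.** **Reproducing the plan's figure.** Inputs from the Sample size row: 10.8% and 13.8%, level 0.05 (two-sided, since a one-sided test would need only 1481), power 0.80.

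- Unpooled: n = (1.96 + 0.842)² × (0.108×0.892 + 0.138×0.862) / 0.03² ≈ 1878 per group.
- Pooled: about 1881. Log-odds scale: about 1890.
- A two-look O'Brien-Fleming design with a look at 30% multiplies n by 1.0006, giving about 1883.

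The stated 1891 is 1891/1881 = 1.005 times the pooled figure, so it holds no clustering allowance. At n = 1891 the standardised effect is θ = 0.03 / √(0.2153/1891) = 2.812, and power is Φ(2.812 − 1.96) = 80.3%.

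**Assumptions (not in the documents).** Ten equal sites of 3782/10 = 378.2 patients, and a residual ICC ρ, after adjustment, of 0.001, 0.005 or 0.01. At the plan's 12.3% incidence the between-hospital SD is √(ρ × 0.123 × 0.877), which is 1.0, 2.3 and 3.3 percentage points. The target difference is 3 points.

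**Variance ratio.** Let aᵢ and bᵢ be the patients on each PN type at site i, with totals A = B = 1891. For the unadjusted contrast:

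DE = [(1−ρ)(1/A + 1/B) + ρ Σ(aᵢ/A − bᵢ/B)²] / (1/A + 1/B)

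1. Five single-type sites per PN type: Σ = 10 × 0.2² = 0.40, so DE = 1 + 377.2ρ.
2. One single-type site of each kind and eight split 50/50: Σ = 2 × 0.2² = 0.08, so DE = 1 + 74.6ρ.
3. All sites 80/20, half leaning each way: Σ = 10 × 0.12² = 0.144, so DE = 1 + 135.2ρ.
4. All sites 50/50: Σ = 0, so DE = 1 − ρ.

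True error of the naive 5% test = 2Φ(−1.96/√DE). Power with the correct variance = Φ(2.812/√DE − 1.96). Random-intercept power comes from the generalised-least-squares information matrix (linear approximation, ICC treated as known, normal reference). Each cell gives the values for ρ = 0.001 / 0.005 / 0.01.

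| Mix | DE | Naive error | Power | Power, random intercept |
|---|---|---|---|---|
| 1. All single-type | 1.38 / 2.89 / 4.77 | 9.5% / 25% / 37% | 67% / 38% / 25% | same |
| 2. Two single-type, eight 50/50 | 1.07 / 1.37 / 1.75 | 6% / 9% / 14% | 77% / 67% / 57% | 78% / 75% / 74% |
| 3. All 80/20 | 1.14 / 1.68 / 2.35 | 7% / 13% / 20% | 75% / 58% / 45% | 76% / 69% / 67% |
| 4. All 50/50 | about 1 | 5% | about 80% | about 80% |

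A beta-binomial simulation (20,000 runs) agrees with the closed-form error rates. In mix 1 it gives 9.2%, 24.6% and 36.9%.

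**Further points on mix 1.**

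- Coverage of a nominal 95% interval is about 90%, 75% and 63%. The limits are too narrow by √DE = 1.17, 1.70 and 2.18.
- On a t reference with 8 df (10 sites less 2), power is 69% even at ρ = 0, then 56%, 31% and 21%.
- More patients at the same ten sites cannot rescue it. Effective n per group tends to 5/ρ, which caps power at 53% for ρ = 0.005 (5/0.005 = 1000) and 30% for ρ = 0.01 (5/0.01 = 500).
- At the interim, 0.30 × 3782 / 10 = 113.46 patients per site gives DE = 1 + 112.46ρ = 1.11, 1.56 and 2.12. Conditional power itself was not computed.

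**The case against.** Four points on the other side carry weight.

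*The harm is conditional.* It needs an uneven PN mix across sites and hospital variation that survives adjustment, and the documents establish neither. Mix 4 shows no problem, and mix 2 at ICC 0.001 costs little. An ICC of 0.01 means a between-hospital SD slightly above the target effect, which nothing in the plan supports or refutes. This stands, and it is why the result is given as a range.

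*The plan already adjusts for hospital features.* These could absorb much of the variation, and the open-ended reference to confounders does not exclude site. But the items are recorded only where available, any of them can be eliminated, and about ten sites support few hospital-level terms. Their p-values would also treat patients as independent evidence on hospital-level variables. They may lower the residual ICC, but they do not model what remains.

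*The figures are illustrations.* They use an unadjusted risk difference, while the planned estimate is an adjusted odds ratio. The random-intercept powers use a normal reference; with t on 8 df, mixes 2 and 3 at ICC 0.01 give about 62% and 55%, although 8 df may be too severe for mixed sites. This stands as a limit on precision, not on direction.

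*A site effect does not cure confounding.* With only single-type sites it widens the limits but cannot separate bag from hospital. With uneven mixing, a random intercept assumes that site risk is unrelated to PN share. The within-site estimate avoids that assumption, at a power of about 71% (mix 2) and 62% (mix 3) at ICC 0.01. This stands, and the fix has to say so. Also, an interim rule that only stops for low conditional power does not itself inflate type I error; the issue there is that conditional power is misjudged.

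**Conclusion.** The concern holds. The 1891 per group is correct on its own inputs, but those inputs assume independent patients, and the primary analysis has no site term or clustered variance to correct for that. The omission itself is certain; its size is not. Over residual ICCs of 0.001 to 0.01 with ten equal sites, the outcome runs from no loss (balanced mix everywhere) to a true error of 37% and power of 25% (single-type sites, ICC 0.01). Partial mixing is not enough protection: 80/20 sites at ICC 0.01 give 20% error and 45% power. Because the gap bears on the validity of the primary limits and on the stated power, it needs to be settled before the analysis.

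**What to change.** - Record a site identifier and the PN type or types used at each site, and state the expected mix.
- Fit the primary model with a site effect that the covariate selection cannot remove. Name one method in advance: a random intercept, or generalised estimating equations clustered on site, with a stated small-sample correction.
- Where sites use both types, also report the PN-type estimate within sites. If all sites are single-type, state that no such estimate exists, that the comparison is between hospitals, and that the site effect widens the limits without removing confounding.
- Restate the 80% as conditional on independent patients. Tabulate power over a range of ICCs and PN mixes, using one reference distribution throughout.
- Use the same site-aware variance for the interim conditional power.

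The cost is SAP wording, two site-level fields and a standard model. The limits will be wider and the stated power less favourable, and with about ten sites the small-sample correction is itself approximate. In return, where sites are mixed, the random intercept recovers much of the lost power at ICC 0.01 on the normal reference: 57% to 74% in mix 2 and 45% to 67% in mix 3.

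### Requiring concomitant antimicrobial treatment does not keep contaminated cultures out of the primary outcome, and the resulting bias can go either way

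*Combined protocol and SAP*

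**What the plan says.** Under Outcome parameters, the primary outcome is "BSI only with concomitant antimicrobial treatment (bacteria and/or candida), thereby excluding patients with contaminations". This is the only step in the plan aimed at contaminated cultures. No section states how many cultures must be positive, how common skin organisms are handled, which clinical signs are needed, or who classifies events.

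Three other entries bear on the point:

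- **Patients.** The population is "treated on any ward and by any medical discipline within the hospital (intensive care unit, normal ward; surgery, non-surgery". Antimicrobials already running are not an exclusion.
- **Parameters for the multivariate analysis.** The list includes "Antibiotic and antimycotic treatment (number, duration, antibiotic free days", under the heading "These parameters will be documented for the multivariate analysis - if available - and the discussion". Neither the indication nor the start date relative to a culture is listed. Antibiotics and antimycotics also appear among the secondary outcomes, under extent of treatment requirement.
- **Exclusion criteria.** The plan excludes "BSI at admission to the participating hospital (not hospitalacquired), i.e., prior to the 3rd calendar day of admission". This is a rule about timing and does not deal with contamination.

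**The concern.** The filter asks whether an antimicrobial was being given, which is a different question from whether the culture reflected infection. Consider two patients, each with one positive culture for a skin commensal that is in fact a contaminant. One is in surgical intensive care and already on antibiotics for peritonitis. The other is on a normal ward without antibiotics. The filter removes the second and can let the first through, so background treatment decides the classification.

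This has two consequences. False events unrelated to the bag raise the event rate in both groups and weaken the odds ratio. And because bag type is not randomised, and sites use three-chamber bags (3CB), hospital compounded bags (HCB) or both, background antimicrobial use and culturing practice may differ by bag type. The outcome rule could then produce part of an apparent bag effect or hide a real one. The same outcome drives the interim stop at 60% conditional power, and the rationale says the results are meant for a pharmaco-economic model.

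**Working it through.** **Inputs from the plan (Sample size).** "Samples size are estimated assuming incidence rates of BSI in MCB of 10.8% and 13.8% in hospital compounded PN, respectively"; "an overall incidence of BSI of 12.3% with a difference between the groups of 3% (± 1.5"; 1891 per group; power 0.80; "taking into account a significance level of 0.05". Sidedness is not stated.

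**Step 1: reproduce the sample size.** Two proportions, pooled variance under the null, two-sided 0.05, no continuity correction:

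n = [1.960·√(2·0.123·0.877) + 0.842·√(0.138·0.862 + 0.108·0.892)]² / 0.03² ≈ 1881 per group.

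The plan's 1891 is 1.005 times this, consistent with a small allowance for the interim analysis. A one-sided test gives 1481 and does not reproduce it. Fixed-sample power at 1891 per group is 80.2%.

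**Step 2: model for false events.** Let p be the BSI rate and f the share of patients without BSI who are counted because of a contaminated culture during unrelated treatment. The counted rate is p + (1 − p)·f.

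The documents do not give f. Assume that 2–6% of patients without BSI have a contaminated culture and that 50–75% of those are on antimicrobials for another reason. Then f runs from 0.02 × 0.50 = 1% to 0.06 × 0.75 = 4.5%.

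**Step 3: same f in both groups, 1891 per group.**

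| f | HCB | 3CB | Difference (points) | Odds ratio | Power |
|---|---|---|---|---|---|
| 0 | 13.8% | 10.8% | 3.00 | 0.756 | 80.2% |
| 1% | 14.7% | 11.7% | 2.97 | 0.771 | 77.1% |
| 3% | 16.4% | 13.5% | 2.91 | 0.795 | 70.9% |
| 4.5% | 17.7% | 14.8% | 2.87 | 0.810 | 66.6% |

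The risk difference shrinks only by the factor (1 − f). Most of the power loss comes from the higher event rate and its variance. The false share of counted events is (1 − p)·f divided by the counted rate: from 0.00862/0.14662 = 6% (HCB, f = 1%) to 0.04014/0.14814 = 27% (3CB, f = 4.5%).

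**Step 4: f differs by bag type (assumed 1% against 3%).**

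- No true effect, 12.3% in both groups: the artefact is 0.877 × (0.03 − 0.01) = 0.0175, about 1.8 points.
- True rates as planned, 3% in HCB and 1% in 3CB: 16.4% against 11.7%, a difference of 4.7 points.
- True rates as planned, 1% in HCB and 3% in 3CB: 14.7% against 13.5%, a difference of 1.2 points and power of 18%.

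**Step 5: alternative reading of the planning rates.** The plan does not say whether its literature rates already include contaminations. Suppose the overall 12.3% does, and the true risk ratio is 10.8/13.8 = 0.783. If 10% of counted events are false, the difference is 2.7 points and power 71.5%. If 20% are false, they are 2.4 points and 61.3%.

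**The case against.** The strongest reply is that the rule is being read harshly. It starts from BSI and adds treatment as a further condition; it does not say that any positive culture counts. The parenthesis naming bacteria and candida might mean treatment directed at the organism. If clinicians dismissed a culture, an abstractor might never record a BSI. This stands in part: the text permits the misclassification but does not show that it will occur. No instruction tells the abstractor to apply the stricter reading, however, and the plan itself presents the treatment condition as what removes contaminations.

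A second reply is that the logistic model adjusts for confounders, and that antimicrobial treatment, reason for ICU admission and severity scores are candidates. This may reduce case-mix differences, but it cannot repair a misclassified outcome. Antimicrobial use is partly a consequence of a true BSI, the listed fields lack indication and timing, the data are collected only where available, and backward elimination may drop the terms.

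A third reply is that the magnitudes are assumed. That is correct. With an equal f of 1% or less, the loss is at most about 3 points of power. If the planned rates and the 3-point difference already describe what this definition would count, power is as planned, and the remaining problem is what the odds ratio means.

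A reader might infer more than the text supports in two ways. One is that the bag effect is necessarily diluted; this holds only if false events are about equally frequent in both groups. The other is that the plan expects background antibiotic use to be common in every patient. Listing a covariate, to be documented where available, is not such an expectation.

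**Conclusion.** The concern holds as a defect of definition. The treatment condition requires coexistence only, nothing else in the plan removes contaminated cultures in patients already treated, and the stated exclusion of contaminations is not assured.

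Size and direction cannot be taken from the documents. Equal false counting at an assumed 1–4.5% is a modest to moderate loss. Unequal false counting is the greater threat: a 1% against 3% split gives an artefact of more than half the planned difference, with unknown sign. The case for changing the definition rests on the primary outcome depending on background treatment, and not on any one assumed figure.

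**What to change.** Define the primary outcome by culture criteria: a recognised pathogen, including Candida, in at least one blood culture; or the same common skin commensal in at least two cultures drawn on separate occasions, with a documented sign of infection. State that an antimicrobial already running for another indication is not evidence of BSI.

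For each patient with a positive culture, record from the chart:

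- organism;
- number and dates of positive cultures;
- signs of infection;
- antimicrobial indication and start date.

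Keep the current treated-BSI definition as a sensitivity analysis. Add a second one that excludes events whose only antimicrobial was already running before the culture.

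The cost is a few extra chart fields for culture-positive patients only, and a lower observed event rate, which should be allowed for in the sample-size assumptions. Some of these fields may be missing from 2014–2015 charts, and the amount missing should be reported by bag type. Some true infections with a single positive commensal culture may be lost; the sensitivity analysis with the current definition shows how far this matters.
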